### 7.2.2 Analysis of Results

The findings of SHI, pulse inversion HI and PDI will be correlated to vascular morphology (i.e., tumor angiogenesis) and other pathological findings; including a) size b) vascularity, and c) type of mass. For cancers, pathological criteria, which will be evaluated, are the stage of the cancer, degree of proliferation and presence or absence of receptors. For the pre and post-contrast enhanced comparisons, dichotomous parameters (e.g., benign/malignant) and ranked data (less, iso, or more intense) will be analyzed with the McNemar test which measures significance of changes in related samples (pairwise comparisons). For variables in which accurate numerical measurement is possible (e.g., perfusion), the techniques will be compared using an ANOVA.

The ability of the imaging tests to distinguish benign from malignant masses will be compared using ROC analysis, while the incremental validity of imaging diagnosis and mammography will be analyzed using logistic regression and ROC analyses [DeLong et al. 1988; Metz 1986; Wagner et al. 2001]. The tests are: x-ray mammography, fundamental grayscale US imaging, PDI, pulse inversion HI and SHI (as well as SHI with CMI-SHI added), while pathology (based on excisional or core biopsies) will provide the reference standard. All studies will be rated on a quasi-continuous scale from 0 to 100, since this has an intuitive probabilistic interpretation and improves the assessment of the characterization capabilities of the imaging modalities compared to using a coarser 6-point scale [Wagner 2001]. Logistical regression techniques will be used to combine the 4 US imaging modes and mammography as well as to incorporate the quantitative parameters into the SHI diagnosis before repeating the ROC analysis. This will allow all possible combinations to be compared to one another (e.g., mammography versus all the US modes combined or mammography and grayscale US versus mammography and grayscale US and SHI, etc.). Differences between ROC curves will be tested by computing Mann-Whitney statistics.

All histopathological variables will be compared to imaging judgments on diagnoses and characteristics of vascularity for the different modalities. When both sets of variables are nominal, chi-square tests will be conducted. When both types of variables are ordinal or continuous, correlations will be calculated. When one type of variable is nominal and one continuous non-parametric rank order tests such as Mann-Whitney U-tests or Kruskal-Wallis tests will be performed [Rosner 1990]. Inter- and intra-observer variability will also be determined by calculating the intraclass correlation coefficient and the kappa statistic [Shrout 1979; McGraw 1996].

Comparisons of sensitivities, specificities and accuracies for diagnosing cancer with the different imaging modalities will be conducted with McNemar's test for correlated proportions (against the histopathological gold standard). All of the statistical analyses proposed for the human clinical trial will be repeated split by racial and ethnic groups to determine if clinically important race/ethnicity differences exist in the ability of 3D SHI to diagnose breast cancer.

Finally, the vascularity measures obtained from the subgroup of up to 85 CD31 stained breast tumor specimens will be compared to the fractional tumor neovascularity data to determine if any correlation exists (in baseline PDI or one of the two contrast enhanced modes). The existence of a linear relationship between ultrasonic and pathologic data will be assessed using single variable linear regression techniques and reverse stepwise multiple linear regression analysis.

All analyses and computations will be performed using NCSS/PASS 2005 and Stata 9.0 (Stata Corporation, College Station, TX), while the study database will be designed and implemented in Filemaker Pro 10.0 (Filemaker Inc, Santa Clara, CA). This database will contain all patient information (except names and other identifiers), including the answers to the questionnaire, and the results of the various US imaging modes as well as the pathology results.

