Appendix A. Investigator Obligations	
Appendix B. Definity Package Insert	

## SYNOPSIS

Protocol Title: Quantitative Subharmonic Breast Imaging

Trial Objectives: The primary objective of this trial is:

- To evaluate if quantitative 3D Subharmonic imaging (SHI) or pulse inversion harmonic imaging (HI) can improve the characterization of benign and malignant breast masses (independently or in combination with other imaging modes) compared to x-ray mammography, fundamental grayscale ultrasound (US) or power Doppler imaging (PDI).

The secondary aim of this trial is:

- To compare quantitative (bifurcations & vessel length) and semi-quantitative (blood pool & parametric imaging) measures of the vascular morphology of breast lesions determined by pathology and by SHI.

Trial Design: This is an open-label, non-randomized trial that will be conducted at two clinical sites (the Breast Imaging Centers at Thomas Jefferson University (TJU) Hospital and University of California, San Diego (UCSD) Hospital). All subjects will receive at most two IV bolus injections of Definity™ (Lantheus Medical Imaging, Billerica, MA), will undergo an unenhanced (baseline) and Definity contrast-enhanced US imaging study for evaluation of a breast mass or breast abnormality without mass, and will be scheduled to undergo a clinically indicated biopsy of the breast lesion under investigation.

Trial Population: This trial will consist of up to 450 adult (18 years of age or older) female subjects who are scheduled for a biopsy of a breast mass or abnormality identified on mammography.

Trial Procedures: Subjects eligible for trial enrollment will be identified by the investigators from among TJU and UCSD's patient population who are referred for a breast biopsy. A full demographic profile, known drug allergies or intolerances, and review of the subject's medical/surgical history will be recorded and reviewed to ensure the subject meets inclusion criteria.

A modified Logiq 9 scanner (GE Medical Systems, Milwaukee, WI) with a broad bandwidth, 3D, linear array will be used to acquire conventional images and subharmonic imaging (SHI).

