## 3. TRIAL DESIGN

This is an open-label, non-randomized trial that will be conducted at two clinical sites (the Breast Imaging Centers at Thomas Jefferson University (TJU) Hospital and University of California, San Diego (UCSD) Hospital). All subjects will receive at most two IV bolus injections of Definity™ (Lantheus Medical Imaging, Billerica, MA), will undergo an unenhanced (baseline) and Definity contrast-enhanced US imaging study for evaluation of a breast mass or breast abnormality without a mass, and will be scheduled to undergo a clinically indicated biopsy of the breast lesion under investigation.

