#### 4.2 Exclusion Criteria

Subjects with any of the following conditions or who have had the following procedures will be excluded from this trial:

- Males
- Females who are pregnant or nursing.
- Patients whose breast lesion is unequivocally a cyst by unenhanced US.
- Patients currently on chemotherapy or with other primary cancers requiring systemic treatment.
- Patients who are medically unstable, patients who are seriously or terminally ill, and patients whose clinical course is unpredictable. For example:
- Patients on life support or in a critical care unit.
- Patients with unstable occlusive disease (eg, crescendo angina)
- Patients with clinically unstable cardiac arrhythmias, such as recurrent ventricular tachycardia.
- Patients with uncontrolled congestive heart failure (NYHA Class IV)
- Patients with recent cerebral hemorrhage.
- Patients with clinically significant and unstable renal and/or liver disease (eg, transplant recipients in rejection)
- Patients who have undergone surgery within 24 hours prior to the study sonographic examination.
- Patients with known hypersensitivity to perflutren
- Patients who have received any contrast medium (X-ray, MRI, CT, or US) in the 24 hours prior to the research US exam
- Patients with cardiac shunts.
- Patients with congenital heart defects.
- Patients with severe emphysema, pulmonary vasculitis, or a history of pulmonary emboli.
- Patients with confirmed or suspected liver lesions.
- Patients with respiratory distress syndrome.
- Patients who have had excisional biopsy/lumpectomy of the current area of interest within the past 6 weeks.

Subject identification will be maintained with a study specific alphanumeric code including the study site, patient number for that specific site (001-225) and the patient's initials.

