#### 6.3 Ultrasound Imaging

The US examinations will be performed by a qualified sonographer. Procedures and equipment for this trial will be used in accordance with typical clinical procedures. In particular, the mechanical index will be set to less than 0.8 on the US scanner. All trial procedures will be conducted in accordance with Good

Clinical Practice. For the ultrasound examination, the patient will be asked to lie in the supine position and a catheter will be placed in a superficial vein (preferably an antecubital vein). Acoustic coupling gel will be applied to the breast area of interest. A baseline US grayscale scan will be used to identify the mass or abnormal area seen by mammography (or another concomitant imaging mode such as US or MRI). Standard PDI of the lesion or target area will also be performed.

Following baseline imaging, patients will receive a bolus, IV injection of 0.25 ml of Definity and the mass or area of abnormality will be imaged with the broad bandwidth linear array (selected in the development phase described above) and a 30 to 40 second digital clip of the 3D pulse inversion HI volume data, covering baseline to beyond peak enhancement, will be acquired. The point of maximum enhancement in the pulse inversion harmonic images will be assessed visually (by the on-site investigators in consensus) and at least 10 seconds of data will be acquired past this time point. Subsequently more sweeps of the abnormality will be stored on the scanner hard drive every 1 to 2 minutes through the period of enhancement (up to 5 minutes).

After a 30 minutes waiting period patients will receive a second bolus, IV injection of up to 20  $\mu$ l/kg of Definity, sweeps of the mass or abnormal area will be made to acquire 3D SHI grayscale volume data through the period of enhancement (up to 2 minutes in our pilot study). It should be noted, that all subjects will be closely monitored by a physician during and following the study (for 30 minutes as recommended by the FDA) [FDA Alert 2007/2008]. Additionally, resuscitation equipment and trained personnel will be in immediate proximity to the patient during the study.

All images (baseline and contrast-enhanced) will be obtained using a broad bandwidth, 3D, linear array, and will include images of the entire area of interest. The entire examination will be recorded as digital loops, as well as on VHS videotape.

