#### 6.5 Surgical Biopsy

All subjects will be scheduled to undergo a breast biopsy (core / excisional / lumpectomy) of the mass or region of abnormality or mastectomy within 30 days after the US study procedure. The date of the

biopsy and the pathology results will be recorded. An experienced pathologist will complete a worksheet for each biopsy specimen. If the patient undergoes a surgical biopsy at TJU, the surgeon ([name]) will mark the transaxial plane of the lesion by sutures upon excision of the breast mass to allow additional data collection from this subgroup of patients in order to partially fulfill the secondary aim of this trial. At UCSD surgical biopsy specimens will be treated according to clinical standard i.e., the imaging plane and the pathology sections will not be matched.

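### Section 7.2.2 pools two sites in the H1 ROC and logistic analyses with no site stratum, so a between-site shift in one imaging mode can bias the AUC difference

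*Combined protocol and SAP*

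**What the plan says.** The trial is "conducted at two clinical sites" (section 3). The subject code described at the end of section 4.2 contains the site, with numbers 001 to 225 at each.

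For H1, section 7.2.2 states: "The ability of the imaging tests to distinguish benign from malignant masses will be compared using ROC analysis". Logistic regression is then used to combine the modes and to "incorporate the quantitative parameters into the SHI diagnosis before repeating the ROC analysis". ROC curves are compared with Mann-Whitney statistics. The section names no site covariate, no stratum and no site-specific AUC. The only planned repeat of the analyses is by race and ethnicity. The one per-site item in the plan is reader repeatability (section 6.6), which adjusts no AUC.

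On scoring, sections 6.6 and 7.2.3 have a single physician read all cases from both sites, and section 7.2.4 bases the H1 power on that reader. Section 6.6 has mammograms read in standard care on the BI-RADS scale. On acquisition, the synopsis says "A modified Logiq 9 scanner (GE Medical Systems, Milwaukee, WI) with a broad bandwidth, 3D, linear array will be used", and section 6.3 says "the mechanical index will be set to less than 0.8 on the US scanner".

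**The concern.** A pooled AUC is the probability that a random malignant case scores above a random benign case. With two sites, some of those pairs set a cancer from one site against a benign lesion from the other. If scores sit higher at one site for reasons unrelated to disease, these cross-site pairs carry the site difference into the AUC. The paired design removes this only when the compared modes shift alike.

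The documents support two routes by which they might not:

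- **Mammography.** Routine-care BI-RADS reading is in effect local, whereas the ultrasound ratings come from one central reader. A difference in BI-RADS use between sites would touch only one side of the SHI-minus-mammography contrast.
- **Quantitative SHI parameters.** These are measurements, so a central reader does not standardise them. Acoustic output has a ceiling but no fixed value.

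At stake is an apparent gain or loss in AUC set against the 0.10 to 0.15 that H1 hopes to show. If site is not handled in advance, any effect seen later can only be dealt with post hoc.

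**Working it through.** **1. The plan's own figure.** Section 7.2.4 gives N = 450, with 400–600 needed for a 10% gain and 167–300 for a 15% gain. It states neither the baseline AUC nor the correlation between modes, so the figures cannot be reproduced uniquely. The Hanley-McNeil variance is Var(A) = [A(1−A) + (m−1)(U−A²) + (n−1)(V−A²)]/(mn), with U = A/(2−A), V = 2A²/(1+A), m malignant and n benign cases. At 90% power, two-sided 0.05 and r = 0.3:

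- 0.75 against 0.85 needs 566 cases at 20% positive and 402 at 30%.
- 0.67 against 0.82 needs 289, 208 and 172 cases at 20%, 30% and 40%.

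The ranges are plausible, and the point below does not depend on them.

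**2. Pooled AUC under a site shift.** Assumptions: equal site sizes, equal-variance binormal scores, within-site AUC A, site 2 shifted by s within-class SDs, malignancy rates p₁ and p₂.

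Pooled AUC = Σᵢ Σⱼ wᵢⱼ Φ((d + sᵢ − sⱼ)/√2), where d = √2·Φ⁻¹(A) and wᵢⱼ = pᵢ(1−pⱼ)/[(p₁+p₂)(2−p₁−p₂)].

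Take A = 0.76, the highest comparator AUC in the pilot data of section 1.1, so d = 0.999.

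- Equal rates, s = 0.5: (0.760 + 0.638 + 0.855 + 0.760)/4 = 0.753, an error of −0.007.
- Equal rates, s = 1: (0.760 + 0.500 + 0.921 + 0.760)/4 = 0.735, an error of −0.025.
- 20% against 40%, s = −1: 0.476×0.760 + 0.143×0.921 + 0.381×0.500 = 0.684, an error of −0.076.
- 20% against 40%, s = +1: 0.476×0.760 + 0.143×0.500 + 0.381×0.921 = 0.784, an error of +0.024.

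| Malignancy rates (site 2 shifted) | −1 SD | −0.5 SD | +0.5 SD | +1 SD |
|---|---|---|---|---|
| equal | −0.025 | −0.007 | −0.007 | −0.025 |
| 20% / 30% | −0.053 | −0.021 | +0.008 | +0.003 |
| 20% / 40% | −0.076 | −0.033 | +0.019 | +0.024 |

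**3. Effect on the difference that H1 tests.** True gain 0.10 (0.76 against 0.86), equal rates, 0.5 SD shift:

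- SHI only: 0.8526 − 0.7600 = 0.093
- mammography only: 0.8600 − 0.7533 = 0.107
- both alike: 0.8526 − 0.7533 = 0.099

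**4. Effect on inference.** With 90 malignant and 360 benign cases, the SEs are 0.0312 (AUC 0.76) and 0.0257 (AUC 0.86). At r = 0.3 the SE of the difference is √(0.0312² + 0.0257² − 0.6×0.0312×0.0257) = 0.0340.

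- No shift: Φ(0.10/0.0340 − 1.96) = 84% power.
- SHI-only shift of 0.5 SD (difference 0.0926): 78%.
- SHI-only shift of 1 SD (0.100 − 0.028 = 0.072): 56%.
- No true gain (0.76 against 0.76), mammography-only shift of 1 SD: an apparent gain of 0.025. Rejection in favour of SHI is about 8% at r = 0 and 12% at r = 0.5, against 2.5% nominal.

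**5. Cost of stratifying.** Two sites with 45 malignant and 180 benign cases each, averaged: SE = √(Var/2) = 0.0313, against 0.0312 pooled. Power is 83.6% against 83.7%. The bias from an additive shift is zero, because no cross-site pair is used.

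**6. Why a site covariate alone is not enough.** Suppose a logistic score carries only site and the rates are 20% and 40%. Its pooled AUC is (2/3)(0.571) + 0.5[(2/3)(0.429) + (1/3)(0.571)] = 0.62, although no imaging information is present. Site must therefore not count toward the AUC.

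**The case against.** The strongest reply is the central reader. One physician rates every ultrasound mode at both sites, so a raw SHI intensity shift does not pass directly into the primary reader AUCs; it enters through the added logistic step. That stands, and it narrows the point to the two routes named.

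A second reply is that the mammography score to be used is itself unclear. Section 6.6 gives BI-RADS, section 7.2.2 says all studies are rated 0 to 100, and section 7.2.3 has blinded reviewers complete a mammography worksheet on a 1-to-5 scale. The mammography route holds to the extent that the routine-care score enters the ROC.

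A third is that a pooled AUC is a legitimate target, namely discrimination on one common scale. That is fair, but the plan does not state this as its choice, and the common scale is not secured for BI-RADS or for the measured parameters.

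Stronger readings are tempting but unsupported:

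- *Each site uses its own acoustic settings and sonographers, so a shift is likely.* One scanner model and one mechanical-index ceiling apply throughout. Section 6.3 says only "The US examinations will be performed by a qualified sonographer", so separate sonographers are an inference.
- *All analyses are pooled.* The CD31 work for H4 uses TJU specimens only, H3 is in dogs, and repeatability is assessed by site.
- *Specimen handling biases H1.* The plan does say "At UCSD surgical biopsy specimens will be treated according to clinical standard i.e., the imaging plane and the pathology sections will not be matched", but plane marking serves the secondary aim. Nothing suggests that it alters the benign/malignant reference diagnosis.

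**Conclusion.** The omission is real: the H1 ROC and logistic analyses have no site stratum, and a shift confined to one mode can bias the AUC difference in either direction. The size is conditional, since the documents give neither a shift nor site-specific malignancy rates; the 20% and 30% in section 7.2.4 are alternative rates for the whole trial. With equal rates and shifts up to 0.5 SD the error is under 0.01, small against 0.10 to 0.15. It becomes material near 1 SD, or when malignancy rates differ between sites. The figure of about −0.08 needs both a 1 SD shift and 20% against 40% malignancy, and it is the error in one AUC, not in the difference. At equal rates a common shift largely cancels, and an SHI-only shift works against SHI. The change is worth making because it costs almost nothing, not because bias has been shown.

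**What to change.** In section 7.2.2:

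- For all H1 comparisons, compute each mode's AUC within site and combine the two (site-stratified AUC, with the DeLong covariance estimated per site). Report the SHI-minus-comparator difference for each site as well.
- Where logistic models combine modes or add quantitative parameters, include site only as a nuisance stratum. Evaluate the combined score with the within-site AUC, so that site itself adds nothing to discrimination.
- Treat site as a stratum in those H2 correlations that use patients from both sites. The CD31 analysis is already confined to TJU and needs no change.

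The cost is analysis wording. Site is already in the subject code, N is unchanged and no new data are needed. Cross-site case pairs are dropped, with the negligible loss of precision shown in step 5 of the working. Estimates for a single site will be less precise and should be presented as descriptive.

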Initial results using contrast enhanced SHI have been promising. As part of a federally funded pilot study using both Definity and Optison (GE Healthcare, Princeton NJ), we have demonstrated, in 14 women with 16 lesions (out of which 4 were cancers) that SHI can detect the slow, small volume blood flow associated with breast tumor angiogenesis [Forsberg et al 2005; 2007]. SHI resulted in an almost complete suppression of tissue signals allowing better visualization of the lesion vascularity relative to baseline power and improved display of small intra-tumoral vessels relative to PDI. The internal morphology of the vascularity associated with the breast masses were also visualized better with SHI than with contrast enhanced PDI. Additionally, we found that the area under the ROC curve for the diagnosis of breast cancer was higher for SHI than for any of the other techniques tested (0.78 versus 0.64, 0.67 and 0.76) [Forsberg et al 2007].

For quantitative analyses, SHI time intensity curves were determined within each lesion using ImagePro Plus software (Media Cybernetics, [name]) [Forsberg et al 2006a]. SHI perfusion estimates were determined using the linear relationship previously established in a canine model [Forsberg et al 2006b]. Perfusion estimates were determined within three regions of interest, (ROIs) encompassing the centre, the periphery or the entire breast lesion. SHI perfusion estimates within the entire lesion were significantly different for malignant and benign tumors ( $p = 0.04$ ) but not for central and peripheral ROIs ( $p > 0.32$ ).

Further quantitative information on the vascular morphology can be extracted post-acquisition by the construction of cumulative maximum intensity (CMI) images from SHI clips. In CMI mode a composite image depicting vascular architecture and blood flow is constructed through maximum intensity projection (MIP) of SHI data over consecutive images [Dave & Forsberg 2009]. Using CMI-SHI the area under the ROC curve was found to be significantly higher than mammography ( $p=0.031$ ) and the highest level of all methods discussed above with an  $ROC=0.90$  [Dave et al 2010]. Using this technique we have

created parametric images of US contrast kinetic data acquired over a specific time sequence (from contrast injection to washout) showing localized variations in these parameters within a plane and potentially providing additional post-acquisition data for lesion differentiation [Eisenbrey et al 2010].

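### The Mann-Whitney test named for ROC differences does not hold the 5% level for nested fitted logistic combinations; the direction of the error depends on the base model and on how many terms are added

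*Combined protocol and SAP*

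**What the plan says.** Section 7.2.2 (Analysis of Results) uses logistic regression for two purposes: to combine four ultrasound modes with mammography, and to "incorporate the quantitative parameters into the SHI diagnosis before repeating the ROC analysis". It then says "This will allow all possible combinations to be compared to one another", and one of its two examples is "mammography and grayscale US versus mammography and grayscale US and SHI". The test named for ROC differences is: "Differences between ROC curves will be tested by computing Mann-Whitney statistics". The same paragraph cites the DeLong method for correlated ROC areas, so I read this as the paired DeLong-type comparison of AUCs.

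The section also says that "the incremental validity of imaging diagnosis and mammography will be analyzed using logistic regression and ROC analyses". It does not say which logistic-regression test would be used. Neither Section 7.2.2 nor the rest of Section 7 describes a validation sample, cross-validation, bootstrap or optimism correction.

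The rating scales differ between sections. Section 6.6 and the Synopsis put ultrasound on 0-100 and mammography on BIRADS. Section 7.2.2 puts all studies on 0-100, and Section 7.2.3 puts all studies on 1 to 5.

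**The concern.** The paired Mann-Whitney test treats the two scores as fixed. In a nested comparison they are fitted scores, and the larger model contains the smaller. If the added term carries no information, two things follow:

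- The two scores rank patients almost identically, so the AUC difference and its estimated standard error both collapse towards zero. Their ratio no longer follows a standard normal distribution.
- Fitting on the same patients pushes the difference upwards. Each added term pushes it further, and so does every tie in the base score that an added rating can break in the fitted direction.

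The first effect makes the test too conservative and the second makes it too liberal. Which one dominates depends on the base and on the number of terms.

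The primary objective (Section 2) includes SHI in combination with other modes, so these comparisons are not peripheral. A non-significant result in the plan's own example could be reported as no added value when a real gain was present. A larger model could be declared better only because it is larger.

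**Working it through.** **Inputs from the documents.** N=450; two-sided 0.05; 20% or 30% malignant, that is 90 or 135 cases (Section 7.2.4); planned AUC gain 0.10-0.15 (Section 7.2.1); pilot AUCs "higher for SHI than for any of the other techniques tested (0.78 versus 0.64, 0.67 and 0.76" (Background). **Assumed:** base AUC of a combination (0.70-0.90 shown), binormal ratings, BIRADS cut-points, subgroup sizes.

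**The plan's own figure.** Section 7.2.4 gives 400-600 patients for a 0.10 gain and 167-300 for 0.15 at 90% power. Baseline AUC and between-mode correlation are not stated, so exact reproduction is impossible. Hanley-McNeil variances with AUC 0.75 and correlation 0.3 give 566 (20% malignant) and 402 (30%) for 0.10, and 227 and 161 for 0.15, which is broadly consistent. For unfitted single-mode ratings the simulated type I error is 4.7-5.3%. Power is 84-96% (20% malignant) or 91-99% (30%) for a 0.10 gain, and at least 99.6% for 0.15. The problem is therefore confined to fitted combinations.

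**How many comparisons are nested.** Five inputs give 31 non-empty subsets and 31×30/2 = 465 pairs. Nested pairs: 3^5 − 2^5 − 31 = 180, adding one (75), two (70), three (30) or four (5) terms. Mammography alone is the base in 2^4 − 1 = 15 of them.

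**Statistics compared.**
- Mann-Whitney/DeLong: z = (A2 − A1)/√(V1 + V2 − 2C), rejecting if |z| > 1.96.
- Likelihood-ratio test (LRT): 2(l2 − l1) against chi-square with df = number of added terms.
- Size of a gain: AUC = Φ(√(D²/2)). A rise from 0.75 to 0.77 takes D² from 2×0.6745² = 0.910 to 2×0.7388² = 1.092. The added rating then contributes √0.182 ≈ 0.43 SD of independent separation.

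**(i) Base with a continuous rating: type I error, N=450, nominal 5%** (simulation ranges over base AUC and malignancy rate)

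| Uninformative terms added | Mann-Whitney |
|---|---|
| 1 | 0.03-0.2% |
| 2 | 0.1-0.5% |
| 3 | 0.6-1.1% |
| 4 | 1.3-2.5% |
| 5 | 2.2-3.5% |
| 7 | 5.5-7.7% |
| 8 | 7.5-10.7% |

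The LRT gives 4.4-6.2% throughout. With mammography in five categories plus a 0-100 grayscale rating as base, one added term still gives 0.07-0.10%, so the plan's own example belongs here even if mammography is on BIRADS.

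**Power with one added term (20%/30% malignant)**

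| Base AUC | Gain | Mann-Whitney | LRT |
|---|---|---|---|
| 0.70 | 0.02 | 17/26% | 82/90% |
| 0.75 | 0.02 | 29/40% | 92/97% |
| 0.80 | 0.02 | 41/57% | 97/99% |
| 0.90 | 0.02 | 76/90% | 100% |
| 0.70 | 0.03 | 37/54% | 95/98% |
| 0.75 | 0.03 | 53/71% | 98-100% |
| 0.90 | 0.03 | 96/100% | 100% |

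Gains of 0.08 or more are detected 98-100% of the time at every base. If SHI alone is 0.10 better than mammography and grayscale (AUCs 0.64-0.76, correlations 0.3-0.7 assumed), the nested gain is 0.073-0.095. Mann-Whitney power is then 95-100%.

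**(ii) Base of mammography alone on BIRADS.** Malignant-benign pairs in the same category count one half in the base AUC, and any added 0-100 rating breaks those ties in the fitted direction. With five categories, type I error is 4-5% for one uninformative mode, 10-11% for two and 21-28% for four, against 4.8-5.8% for the LRT. Other cut-points with four or five categories give 1.3-5.0%, 3.4-13.9% and 8-36%. For a true one-term gain of 0.02 in one such setting, power was 57/79% against 93/97% for the LRT.

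**(iii) Quantitative SHI parameters.** Section 7.2.2 does not list them. The Synopsis names "quantitative (bifurcations & vessel length) and semi-quantitative (blood pool & parametric imaging) measures of the vascular morphology of breast lesions", which makes four, and Section 7.2.1 adds perfusion for a fifth. Seven results only if perfusion enters for three regions, as in the pilot: "Perfusion estimates were determined within three regions of interest, (ROIs) encompassing the centre, the periphery or the entire breast lesion". The table above shows 2.2-3.5% at five terms and 5.5-10.7% at seven or eight.

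**Race/ethnicity repeats (sizes assumed).** One term, gain 0.10, base 0.75: N=150 gives 79/92% against 100% for the LRT; N=90 gives 48/64% against 97/99%.

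**The case against.** The strongest case on the other side has four parts.

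- **The remedy is partly in the plan.** Logistic regression is already assigned to incremental validity, and testing the added coefficient is a natural part of that. This stands as far as it goes: such a test is not excluded. But none is specified, and the sentence on ROC differences makes no exception for fitted combinations.
- **The consequence is limited.** The planned 0.10-0.15 effect is barely touched, and no section says that a gain of 0.02-0.03 matters. This stands and limits the weight of the point. At a high base AUC even those small gains are mostly detected.
- **Seven or eight parameters is speculative.** This stands. The Synopsis list belongs to the secondary aim, and the pilot found only the whole-lesion perfusion estimate discriminating. Part (iii) is conditional.
- **Subgroup sizes are assumed.** This also stands.

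Two stronger readings are tempting. A reader might infer that the test is always too conservative for mode combinations, or that only the number of terms sets the direction. The BIRADS scale in Section 6.6 contradicts both: with mammography alone as base, adding modes makes the test liberal. A reader might also infer that the primary hypothesis or the sample size is undermined. It is not. Section 7.2.4 sizes a comparison of ROC curves read by the primary reader, and the combined grayscale-and-SHI reads of Section 6.6 are unfitted ratings.

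**Conclusion.** The point holds and should be fixed before analysis: the named test is invalid for nested fitted combinations.

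- The severe conservatism in the plan's own example is well supported: about 0.1% type I error, and power of 29/40% instead of 92/97% for a 0.02 gain at base AUC 0.75.
- The liberal behaviour with mammography alone as base is firm in direction once several modes are added. Its size depends on the BIRADS categories and cut-points, which are assumed.
- The liberal behaviour with many quantitative parameters depends on a count that the plan does not give.

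The verdict rests on three readings: Mann-Whitney statistics means the paired DeLong-type test, models are fitted and evaluated on the same patients, and ultrasound ratings are on 0-100. If the 1-to-5 scale of Section 7.2.3 were used instead, ties would matter in more comparisons and the figures in (i) would not carry over.

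**What to change.** 1. For nested pairs, test the added mode or parameters by the likelihood-ratio test of the added coefficients.
2. Report the AUC gain beside it with bootstrap optimism correction, refitting the whole model in each resample. Use the same correction for fitted non-nested comparisons, such as mammography against all ultrasound modes.
3. List a short set of quantitative parameters in advance, and state one rating scale per modality.
4. Keep the Mann-Whitney/DeLong test for unfitted ratings.
5. Apply the same rules in the race/ethnicity repeats and give the malignant count per group. A test within a group does not compare groups.

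**Cost.** SAP wording and code, with no new data. Combination AUCs come out slightly lower. For a best-possible gain of 0.03 at N=450 with 90 malignant, the apparent gain is 0.032, 0.037 and 0.041 with one, five and seven added terms. The corrected gain is 0.029, 0.024 and 0.022, against 0.029, 0.023 and 0.020 truly delivered by the fitted equation. In small groups the correction is incomplete: at N=150 with 30 malignant and seven terms, apparent 0.059, corrected 0.009, true 0.001.

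The likelihood-ratio test shows that information is added, not how much. It is slightly liberal in small groups (up to about 7%) and loses power as terms are added: for a 0.02 gain, 81/90% with five terms and 76/85% with seven.
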